#### Sensitivity 2.

Multiple imputation will be used to impute data in each of the study groups. A progressive penalty of  $\delta_i = k_i \times \log(OR)$  will be added to imputed

values in ZNS arm where (i)  $OR$  is the Odds ratio estimate for ZNS as compared to Placebo from the primary logistic regression analysis and (ii)  $k_i = 1, 0.95, 0.90, \dots, 0.05, 0, 1.05, 1.10, \dots$  thus  $k$  ranges from 1 (equivalent to MI approach based on MAR) to 0 (or higher), until the conclusion of the primary analysis is overturned (i.e.,  $p < 0.05$  is lost at, this value of  $k_i$  being the ‘tipping point’). Rubin’s method will be used to combine the primary endpoint treatment effects across imputations for each value,  $k_i$ , of the penalty. Forest plots will be used to graphically display the penalty value that results in loss of statistical significance.

SAS code sample for Sensitivity analysis is provided below:

```

**Step 1: Generate 10 datasets by imputing the missing data**;

PROC MI DATA=X SEED=<value> NIMPUTE=10 OUT=MI_OUT1 NOPRINT;
CLASS GROUP;
VAR AGE PTA LSurg.....;
FCS LOGISTIC(PTS);
RUN;

**Step 2: Generate 10 complete datasets from the 10 monotonized
datasets in Step 1 for missing values in the drug arm,
subtract DELTA derived above from their imputed data.**;
proc mi data=YYY NIMPUTE=1 SEED=<value> OUT=YYY_shift;
by group;
class group;
var AGE PTA LSurg.....;
monotone method=logistic;
mnar adjust(PTS / shift=DELTA adjustobs=(group='1'));
run;

**Step 3: Apply the primary MMRM to the 10 complete datasets in
Step 2**;
proc genmod data=YYY_shift descending;
by _imputation_;
class group;
model PTS = group AGE PTA LSurg.....;
ods output GEEModPEst=gmparms;
run;

**Step 4: Obtain the pooled inference from 10 sets of estimates
from Step 3**;

PROC MIANALYze PARMS=GMPARMS COVB=GMCovB PARMINFO=GMPINFO WCOV
BCOV
TCOV;
MODELEFFECTS group;
RUN;

```

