2.7 Sample Size Determination for The Primary Efficacy Outcome Measure

Calculation of sample size for this study is based on a balanced design and a one-sided significance level of 0.025. We estimate that among officers identified as being at high risk for permanent hearing loss due to having TTS, the proportion of PTS positive officers 30 days (+/- 3 days) after shooting will be 50%. This is the proportion of PTS positive officers we expect to observe in the placebo group. Thus, for the primary outcome, we estimated that 66 officers per group will provide us with 80.5% power to detect a 50% reduction in the proportion of PTS positive officers (from 50% to 25%) at the 1-sided alpha level of 0.025. A planned total of 132 subjects is to be enrolled and randomized.

We will make all the needed efforts to eliminate drop outs, and due to short term-follow-up of the study subjects in a period we do not expect any drop-outs or lost to follow-up.

All sample size calculations were carried out using PROC POWER procedure in SAS 9.4.

3 Study Outcomes

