3.2 Primary Efficacy Outcome

The primary efficacy outcome will be the proportion of PTS positive subjects defined as the ratio of PTS-positive subjects to total number of subjects in each study arm/group. PTS positive will be defined as all subjects who in audiogram are identified as having a permanent threshold shift (PTS) of ≥ 10 dB HL increase at any frequency from 2-6 kHz after shooting as compared to baseline audiogram. A SAS code will be written to code as PTS positive all the officers for whom the difference at any frequency from 2-6 kHz in hearing thresholds (30 days (+/- 3 days) post shooting - Baseline) will be ≥ 10 dB HL in at least one of the ears. If this difference is less than 10 dB then the officers will be coded as non-PTS positive.

To date, there are no reports of ZNS being associated with hearing damage or loss, so the hypothesis for this study will be a one-sided hypothesis.

For the primary outcome measure, the null and alternative hypotheses are provided below.

Comparison of the proportion of PTS-positive subjects between ZNS group and Placebo

$$H_0: p_{ZNS} - p_{Placebo} = 0 \quad H_A: p_{ZNS} < p_{Placebo}$$

We hypothesize that ZNS will reduce the proportion of PTS-positive officers by an absolute difference of 25% as compared to placebo. Our one-sided hypothesis is supported by animal studies, and lack of any evidence of hearing loss as a side effect of ZNS in human studies.

Hypothesis testing for the primary outcome will be performed at the one-sided alpha level of 0.025.

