5.2 Missing Data

Every attempt will be made to ensure data completeness. We do not anticipate much loss to follow-up because of the relatively short time follow-up interval. Conservatively, we would estimate that fewer than 5% of subjects will drop out/withdraw from the study. The participant will be withdrawn from the study follow-up and procedures if the participant withdraws consent, or the sponsor decides to close the study.

Data loss, if any, would almost likely be due to subjects refusing to complete or not returning at all for the post-shooting assessment of PTS 30 days (+/- 3 days). If the subject reschedules the post-shooting appointment for a later date for any reason, and if this delay is within 30 days of the scheduled date, the data will be considered valid and used in the efficacy analysis. Any measure outside this time window of +30 days will be defined and considered as missing data.

Missing PTS at 30 days will be imputed using SAS PROC MI procedure within each treatment group using the distribution implied by the non-missing data for the specific treatment group. The SAS code below using MICE via the Fully Conditional Specification (FCS) statement will be used to impute the missing data under the missing at random (MAR) assumption.

```
PROC MI DATA=X SEED=<value> NIMPUTE=10 OUT=MI_OUT1 NOPRINT;
  CLASS GROUP;
  VAR AGE PTA LSurg....;
  FCS LOGISTIC(PTS);
  RUN;
```

The estimates of the analysis of the 10 imputed datasets will be then combined following Rubin's rules using PROC MIANALYZE procedure in SAS which will be of the form:

```
PROC MIANALYZE PARMs=GMPARMS COVB=GMCOVB PARMINFO=GMPINFO WCOV BCOV
  TCOV; / *dataset "gmparms" contains the estimates and associated standard errors
  for the mean parameters from each of the M=10 imputed data sets.
  dataset "gmcovb" contains the asymptotic covariance matrices
  dataset "gmpinfo" contains parameter info*/
  MODELEFFECTS group;
  RUN;
```

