Multiple imputation will be used to impute data in each of the study groups. A progressive penalty of $\delta_i = k_i \times \log(OR)$ will be added to imputed values in ZNS arm where (i) OR is the Odds ratio estimate for ZNS as compared to Placebo from the primary logistic regression analysis and (ii) $k_i = 1, 0.95, 0.90, \dots, 0.05, 0, 1.05, 1.10, \dots$ thus k ranges from 1 (equivalent to MI approach based on MAR) to 0 (or higher), until the conclusion of the primary analysis is overturned (i.e., $p < 0.05$ is lost at, this value of k_i being the 'tipping point'). Rubin's method will be used to combine the primary endpoint treatment effects across imputations for each value, k_i , of the penalty. Forest plots will be used to graphically display the penalty value that results in loss of statistical significance.

SAS code sample for Sensitivity analysis is provided below:

```
**Step 1: Generate 10 datasets by imputing the missing data**;

PROC MI DATA=X SEED=<value> NIMPUTE=10 OUT=MI_OUT1 NOPRINT;
CLASS GROUP;
VAR AGE PTA LSurg....;
FCS LOGISTIC(PTS);
RUN;

**Step 2: Generate 10 complete datasets from the 10 monotonized datasets in Step 1 for
missing values in the drug arm,
subtract DELTA derived above from their imputed data.**;
proc mi data=YYY NIMPUTE=1 SEED=<value> OUT=YYY_shift;
by group;
class group;
var AGE PTA LSurg....;
monotone method=logistic;
mnar adjust(PTS / shift=DELTA adjustobs=(group='1'));
run;

**Step 3: Apply the primary MMRM to the 10 complete datasets in Step 2**;
proc genmod data=YYY_shift descending;
```

```
by _imputation_;
class group;
model PTS = group AGE PTA LSurg.....;
ods output GEEModPEst=gmparms;
run;

**Step 4: Obtain the pooled inference from 10 sets of estimates from Step 3**;

PROC MIANALYze PARMS=GMPARMS COVB=GMCOVb PARMINFO=GMPINFO WCOV BCOV
TCOV;
MODELEFFECTS group;
RUN;
```

7.1.2 Analysis for secondary outcome measures.

The focus of the study is to determine efficacy of ZNS for treatment of acute hearing loss based on the testing of the hypothesis for the primary outcome. In addition, we will also conduct analysis to evaluate other important audiologic measures. The secondary outcome measures are key audiological and clinical assessments of hearing loss, and include: Audiometric TTS, DPOAEs, Ultra-high frequency audiometry, ECochG, and WIN testing 30 days (+/- 3 days) after shooting, and are measured as continuous level variables. We do not plan any adjustment of alpha error for multiple comparisons.

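### The Sensitivity 2 program does not carry out the tipping-point analysis described: it would not run as printed, and if patched only enough to run, its penalty changes nothing

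*SAP*

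**What the plan says.** SAP 7.1.1 announces Sensitivity 2 as a logistic-regression tipping-point analysis. A penalty k × log(OR) is applied to imputed ZNS values, results are pooled by Rubin's rules at each k, and k is varied until significance at 0.05 is lost. A four-step SAS sample follows. Protocol 12.2.1 prints the same text and code.

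- Step 1 is headed "Generate 10 datasets by imputing the missing data". It runs PROC MI with ten imputations and `FCS LOGISTIC(PTS)`, and writes `MI_OUT1`.
- Step 2 has the comment "Generate 10 complete datasets from the 10 monotonized datasets in Step 1" and says delta is subtracted from the imputed ZNS data. It reads a data set `YYY`, runs by group, and applies "mnar adjust(PTS / shift=DELTA adjustobs=(group='1".
- Step 3 is labelled as the primary MMRM. It is a PROC GENMOD model for PTS with no distribution or link, and it asks for "ods output GEEModPEst=gmparms".
- Step 4 pools with PROC MIANALYZE, reading `GMPARMS`, `GMCOVB` and `GMPINFO`.

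On the expected amount of missing data, SAP 5.2 says "fewer than 5% of subjects will drop out/withdraw from the study".

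**The concern.** A delta adjustment works only if the outcome is still missing when the shift is applied. Here Step 1 is headed as imputing the missing data and carries no monotone-only option, yet Step 2 treats its output as merely made monotone. If PTS is already complete on entry to Step 2, the shift has nothing to act on and the search over k returns one answer throughout.

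The steps also do not connect with each other, and Step 3 does not match the announced logistic model.

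Sensitivity 2 is the only analysis in the plan that asks how far the missing ZNS outcomes must depart from the assumed model before the primary conclusion fails. If it is repaired after unblinding, it becomes post hoc. If it is repaired only until it runs, a flat line over k could be read as robustness.

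**Working it through.** **Reproducing the plan's own figure.** The documents give no numerical result for Sensitivity 2. The nearest stated figure is the power: "we estimated that 66 officers per group will provide us with 80.5% power to detect a 50% reduction" ("from 50% to 25%) at the 1-sided alpha level of 0.025"). The continuity-corrected arcsine (Walters) approximation, with c = 1/(2 × 66), is

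z = √132 × [arcsin√(0.5 − c) − arcsin√(0.25 + c)] = √132 × (0.7778 − 0.5323) = 2.821

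Power = Φ(2.821 − 1.960) = 80.5%. Exact enumeration of Fisher's test gives 81.3%. The stated figure reproduces.

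**Reading the code.** SAS was not run, so these points come from reading the steps against each other.

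1. PTS is the target of a logistic imputation but is not in CLASS, nor in the visible part of VAR.
2. Step 1 writes `MI_OUT1`; Step 2 reads `YYY`, which is never defined.
3. Step 2 runs by group and not by `_Imputation_`, so the ten sets are not kept apart.
4. Step 3 requests a GEE table without a REPEATED statement.
5. `GMCOVB` and `GMPINFO` are read in Step 4 but never created.
6. With no DIST= or LINK=, GENMOD fits its default normal/identity model.

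Points 1 to 5 stop the program short of a pooled p-value.

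**If it is patched only enough to run**, and `YYY` is the Step 1 output as the Step 2 comment says, no PTS is missing in Step 2 and the shift is inert. I emulated the steps outside SAS: logistic imputation within arm, ten imputations, Rubin's rules, and one simulated age covariate. The counts are assumptions. Fewer than 5% of 132 means at most 6 missing (0.05 × 132 = 6.6). P-values are two-sided; in the direction of benefit, 0.05 corresponds to one-sided 0.025. The shift is k × |log OR| against ZNS.

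| Observed, placebo v ZNS | Missing | As printed, every k from 0 to 8 | Shift applied at imputation |
|---|---|---|---|
| A: 31/63 v 16/63 | 3 per arm | 0.0069 | 0.0106 (k=1), 0.0188 (k=8): no tip |
| B: 30/63 v 18/63 | 3 per arm | 0.0312 | 0.0453 (k=1), 0.0517 (k=1.5), 0.0684 (k=8): tips |
| C: 33/66 v 16/60 | 6 in ZNS | 0.0064 | 0.0179 (k=1), 0.0498 (k=4), 0.0532 (k=8): tips just above k=4 |

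**Hand check of B.** log OR = ln[(18/45)/(30/33)] = ln 0.44 = −0.821. At k = 1 the shifted ZNS log-odds are ln(18/45) + 0.821 = −0.095, a probability of 0.476, which is the placebo rate 30/63. At very large k all three missing ZNS officers are positive (21/66), and the placebo arm is expected at 30 + 3 × 0.476 = 31.43 of 66. Then:

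- log OR = ln[(21/45)/(31.43/34.57)] = −0.667
- SE = √(1/21 + 1/45 + 1/31.43 + 1/34.57) = 0.361
- z = −1.845, p = 0.065

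So a tip exists in B whatever the seed. Its exact k does depend on the seed with ten imputations: a repeat of B with 2,000 imputations and no covariate gave p = 0.0482 at k = 2 and 0.0626 at k = 4.

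**Normal v logistic in Step 3.** In A without a shift, the effect is −0.234 (risk difference) instead of −1.03 (log OR), and p is 0.0053 instead of 0.0069. The scale changes; the p-value hardly does.

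**Direction of the penalty.** The text adds k × log(OR) while the code comment subtracts it. For a protective OR, log(OR) is negative, so a working shift that is added favours ZNS. In B, p falls from 0.0312 to 0.0258 at k = 1 and 0.0180 at k = 8. The text also labels k = 1 as MAR, but with a shift of k × log(OR) the unshifted case is k = 0.

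**The case against.** The best defence is that this is a sample with ellipses and placeholders. The prose does specify a penalty on imputed ZNS values and pooling at each k, and SAP 11 requires specifications, independent double programming and senior review. Code that does not run would be caught there. The Step 2 comment also speaks of missing values in the drug arm, so the author probably meant PTS to be still missing at that point.

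Part of this stands. The inert shift is conditional on `YYY` being the Step 1 output. But the comment says that it is, and the fault lies in the sequence of steps as well as in the syntax. Double programming follows the protocol and SAP, so two programmers could agree on the same wrong sequence.

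A reader might infer that the analysis would look robust at every penalty. The documents do not support that. As printed there is no pooled p-value at all, and after a minimal patch a flat p looks robust only if the unshifted result is already significant.

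A reader might also offer 33/66 v 20/66 (one-sided Fisher p = 0.0163) becoming 33/66 v 23/66 (p = 0.0563) when three ZNS officers turn positive. That needs all three to have been imputed negative. The observed 33/66 v 20/63 gives p = 0.0267, above 0.025 before any penalty, so it does not show a tip.

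Nor does the normal model in Step 3 cause the flat result. And Sensitivity 2 is not the only safeguard: Sensitivity 1 addresses the same missing outcomes, though without searching over a range of penalties.

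**Conclusion.** The point holds in this form: the Sensitivity 2 program in both documents does not implement the analysis that the text describes. As printed it would not reach a pooled result. Patched only enough to run, it returns the same p at every k and can hide a tipping point that exists within the plan's own allowance for missing data.

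The size is limited. The hidden tip appears when the effect is borderline (scenario B) or when all six losses fall in the ZNS arm (scenario C). With a strong effect (scenario A) even a correct shift does not tip. The scenario counts are assumed, the crossing point in k is sensitive to the seed, and procedure behaviour was read from the code and not tested in SAS. The wrong Step 3 model is a separate error of scale with little effect on p. The primary analysis is untouched: "Hypothesis testing for the primary outcome will be performed at the one-sided alpha level of 0.025", by Fisher's test. The code should be corrected before unblinding, as a matter of priority below any change to the primary analysis.

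**What to change.** Replace the four steps in SAP 7.1.1 and Protocol 12.2.1, and align the text:

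1. For each k, impute PTS once (ten imputations) from data in which it is still missing, with the MNAR shift for the ZNS arm inside that PROC MI call. Alternatively, make Step 1 monotone-only so that PTS is still missing in Step 2. Put PTS and GROUP in CLASS and VAR.
2. Define k = 0 as MAR, direct the penalty against ZNS, and make the text (added) and the code comment (subtracted) agree. Without this, a working shift added as written moves the result in favour of ZNS.
3. Fit a binomial model with logit link by `_Imputation_`, with ODS output that matches what MIANALYZE reads, and pool the group coefficient. Remove the MMRM label.
4. State the tipping criterion on the one-sided 0.025 scale of the primary test.
5. Test the program on dummy data with known missing values and confirm that the pooled estimate moves with k.

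Given the seed dependence seen in scenario B, consider more than ten imputations for this analysis. The cost is text edits in two documents and a few hours of programming; no data collection or sample size changes.

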### **3.1b Enrollment Inclusion Criteria**

1. Observed audiometric TTS  $\geq$  10 dB HL at 2, 3, 4 and/or 6 kHz

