### **5.4 Follow-Up Assessments (Visits 3, 4 and 5)**

The follow-up assessments will occur after training and include the following tests or procedures:

1. Audiogram and DPOAEs to measure for TTS and auditory changes, as soon as possible after the training session. The exact time of testing following training operations will be documented. A clinical ear exam will be completed prior to the audiogram and DPOAEs. (follow-up visit 3 and 5).
2. Baseline environmental/ambient sound measurements will be recorded at the start of each test session, including the peak ambient noise level and the average noise level (follow-up visit 3 and 5).
3. Collection of blood for laboratory testing to include an electrolyte panel, BUN, Cr, ALT, and AST. This will occur within 12-24 hours following drug intake (follow-up visit 4).
4. Cognitive assessments within 24 hours following drug intake, including (follow-up visit 4):
  - a. Digit-symbol substitution test (processing speed)
  - b. Verbal fluency (working memory, speech/language)
  - c. Stroop (Executive function, inhibition)
  - d. List Learning task/RBANS (memory)

Additionally, after each officer is asked about potential study-related side effects for safety monitoring, they will be asked a question regarding their feeling of safety on the job, i.e. they will be asked *“if they feel safe partaking in required responsibilities associated with their job at this time or not?”*

5. Completion of LENS-Q 1-minute noise screening for noise exposure questionnaire (follow-up visit 5).
6. Audiogram, ECochG, DPOAE, and WIN testing 30 days (+/- 3 days) after each training session to assess for PTS and auditory changes, only if TTS is observed from #1 (visit 5).
7. Documentation of adverse events at all follow-up visits (5-30 minutes post, within 24 hours and at 30 day visit) (follow-up visit 3, 4 and 5).

Follow-up assessments will be planned at the stated time points; actual follow up times may vary due to patient logistics and compliance.

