2.5 Treatment Assignment and Blinding

The study will be “masked” or “blinded” in the sense that all the study subjects and the study team members will be blinded to the assignment in the study groups. Only the pharmacist who will prepare the study drug kits and the unblinded statistician will have access to the kit assignments. The Medical Monitor will be contacted. A copy of the randomization list with study ID assignments will be saved in a limited access folder on a secure network server at Pharm-Olam. The Medical Monitor will be contacted in emergent medical cases when knowing the treatments assignment is mandatory for clinical care of the study subject.

The data will be presented without having the treatment assignments of individual study subjects made known to study team members including the study PI. Table shells will be blinded. If DSMB members find any safety issues, they may request specific unblinded data. Table shells for DSMB (content and formats) will be agreed upon prior to start of study.

Subjects will receive one time dose of oral ZNS or matching placebo after training if TTS is identified on audiogram 5-30 minutes after shooting. Subjects will be instructed to take study drug without food. We will recommend that capsules be swallowed whole per the current approved labeling.

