3.3 Secondary efficacy outcomes

The study is designed to test the null hypothesis associated with the primary efficacy measure. Nevertheless, it provides a great opportunity to evaluate the impact of ZNS on other audiometric and clinical measures:

- DPOAEs: Distortion product otoacoustic emissions will be measured at baseline

(before shooting), as well as within 5-10 minutes after shooting and 30 days (+/-3 days) post-shooting (for officers with positive TTS) to measure both temporary and permanent changes in DPOAE amplitude relative to baseline. A change is noted in DPOAE amplitude at any frequency that is significantly greater than the stability of each measurement (i.e., 95% confidence interval of each measurement do not overlap).

- Ultra-high frequency audiometry: Ultra-high frequency audiometry (10-14 kHz) will be measured at baseline (before shooting), 30 days (+/-3 days) after shooting (for officers with positive TTS) to measure for both temporary and permanent high frequency audiometric changes. A significant change is defined for any frequency that is greater than 5 dB HL from baseline thresholds.
- ECochG: Electrocochleography will be measured at baseline (before shooting) and 30 days (+/-3 days) after shooting (for officers with positive TTS) to measure for changes in ECochG AP amplitude, latency and width.
- WIN testing: The Words-In-Noise test will be administered at baseline (before shooting) and 30 days (+/-3 days) after shooting (for officers with positive TTS). The respective scores will be converted to Z-scores to evaluate for any change in scores relative to baseline.

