Analysis of variance (ANCOVA) will be used for comparison of outcome measures between each of the ZNS groups and placebo study group after controlling for baseline value, age, pre-op hearing dichotomized to: normal to minimal hearing loss and slight to mild loss, noise exposure history dichotomized to: high risk and low risk, average post-shooting TTS.

Statistical analyses will be conducted using the SAS software (SAS Institute Inc., Cary, N.C.,

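### The day-30 DPOAE ANCOVA omits the Visit 3 post-shooting DPOAE, which gives up some precision on one secondary outcome

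*SAP*

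**What the plan says.** SAP 7.1.2 treats the secondary outcomes alike. DPOAE is among them, with "ECochG, and WIN testing 30 days (+/- 3 days) after shooting, and are measured as continuous level variables". Each is compared between arms by ANCOVA "after controlling for baseline value, age, pre-op hearing dichotomized to: normal to minimal hearing loss and slight to mild loss", then "noise exposure history dichotomized to: high risk and low risk, average post-shooting TTS". The list stops there, and Protocol 12.2.2 gives the same one.

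DPOAE has three time points. SAP 3.3 places the baseline before shooting, with further readings "as well as within 5-10 minutes after shooting and 30 days (+/-3 days) post-shooting". Protocol 5.4 schedules the Visit 3 tests as "Audiogram and DPOAEs to measure for TTS and auditory changes, as soon as possible after the training session", and the calendars in Protocol 9.0 and SAP 2.6 show DPOAE at that visit. Randomisation and dosing belong to the same visit: the capsule is given "after training if TTS is identified on audiogram 5-30 minutes after shooting" (SAP 2.5).

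TTS is a pure-tone quantity. The enrolment criterion in Protocol 3.1b is worded as "Observed audiometric TTS" of at least 10 dB at one or more of 2, 3, 4 and 6 kHz.

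Post-shooting measurements do appear elsewhere in the plan. The pharmacogenetic sections (Protocol 12.5, SAP 7.1.3) use hearing functions measured straight after the range. Protocol 4.0 lists the rate of DPOAE shift, as a sign of temporary cochlear change, among the secondary efficacy outcomes.

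**The concern.** Putting average TTS in the model shows that the authors want to adjust for how badly the index exposure injured each officer before treatment could act. For audiometric outcomes that covariate is on the outcome's own scale. For DPOAE it comes from a different test, and the only DPOAE term, the Visit 2 value, predates the noise and cannot reflect it. The reading that shows how far each officer's emission fell is already scheduled for every randomised officer but is left out.

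Differences between officers in the initial DPOAE fall, so far as they persist to day 30 and TTS does not capture them, then stay in the residual error. The day-30 comparison is less precise than the collected data allow, and a chance imbalance between arms in initial DPOAE injury is only partly adjusted for.

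**Working it through.** **1. What each covariate can carry for day-30 DPOAE.**

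| Term | Taken after the noise? | On the DPOAE scale? | In the ANCOVA? |
|---|---|---|---|
| Visit 2 DPOAE | no | yes | yes |
| Average post-shooting TTS | yes | no | yes |
| Visit 3 DPOAE | yes | yes | no |

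Age, hearing class and noise stratum are the other planned covariates. None of them measures the index exposure's effect on emissions.

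**2. The plan's own figures.** There is no DPOAE power, SD or correlation to reproduce. The nearest stated figure is the primary one in SAP 2.7: 66 per arm, 50% against 25%, one-sided 0.025, power 80.5%. An arcsine approximation with continuity correction gives 80.53%, and full enumeration of Fisher's test gives 81.3%. That figure is sound and is not in question here.

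**3. Effect of adding the reading.** Let r be the partial correlation between Visit 3 and day-30 DPOAE given the planned covariates. Residual variance is multiplied by 1 − r² and the standard error by √(1 − r²). For illustration, take an effect that has 80% power under the planned model at two-sided 0.05. The SAP states neither level nor sidedness for secondary outcomes, so both the 80% and the 0.05 are assumptions. Power with the added term is Φ(2.80/√(1 − r²) − 1.96).

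| Assumed r | Variance factor | SE reduction | Power, from 80% |
|---|---|---|---|
| 0.1 | 0.99 | 0.5% | 80.4% |
| 0.3 | 0.91 | 4.6% | 83.6% |
| 0.5 | 0.75 | 13.4% | 89.9% |

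Where r would lie is unknown. A simulation on assumed variance components, with baseline and TTS already in the model, gave r of about 0.23 when none of the acute shift persisted to day 30. It gave 0.47 to 0.68 when 30% to 70% persisted. These values show that the range is possible; they are not estimates.

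**4. Break-even.** The planned model has 7 parameters (intercept, treatment, five covariates), so 132 − 7 = 125 residual degrees of freedom at full enrolment. One added term costs a factor of 125/124 = 1.008, which is recovered when r² exceeds 1/125 = 0.008, that is r of about 0.09. With a missing-reading indicator as well, the requirement is r² above 2/125 = 0.016, or r of about 0.13.

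**5. Sample actually analysed.** It will be below 66 per arm. Dropout just under the 5% ceiling in SAP 5.2 would leave about 66 × 0.95 = 62.7. Protocol 3.2 also removes from the DPOAE analysis anyone with emissions absent at more than 4 of 10 frequencies, a number the documents do not predict. With 80% as the fixed starting point the power column does not depend on n, but the effect it refers to does: 0.488 residual SD at 66 per arm and 0.499 at 63.

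**6. Readings that cannot be used.** If only a fraction f of readings is known to be pre-dose and the rest are set to a constant with an indicator, the average variance factor is f(1 − r²) + (1 − f) = 1 − f·r². For example, at f = 0.5 and r = 0.5 the reduction is 12.5%, not 25%.

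**The case against.** The strongest objection concerns timing. No section says whether the Visit 3 DPOAE is recorded before the capsule is taken. Dosing follows the audiogram; SAP 3.3 places the DPOAE at 5–10 minutes after shooting, the calendar at 5–30 minutes, and Protocol 5.1 says the recording takes about 20 minutes. Adjusting for a post-dose reading would be wrong, because treatment could have affected it. This stands, and it limits the covariate to readings documented as pre-dose.

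Second, Protocol 4.0 compares the DPOAE shift between arms as an outcome, so using the same reading as a covariate looks contradictory. A pre-dose reading remains a valid covariate whatever else it is listed as, but the plan should say which role it has. The ANCOVA term also does nothing for the shift-positive rate in Protocol 4.0; it helps only the continuous amplitude.

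Third, every size above rests on an assumed r and an assumed 80% starting power. That stands too. Protocol 1.5's remark that OAEs are more sensitive than thresholds does not settle it: the remark is tied to the risk of future hearing loss, and does not show that TTS poorly captures an acute DPOAE fall.

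A reader might infer that the plan never uses the post-shooting reading. The pharmacogenetic plan and Protocol 4.0 show otherwise; it is absent only from the efficacy ANCOVA. A reader might also infer that the planned comparison is biased. It is prespecified and protected by randomisation, so it is not.

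**Conclusion.** The omission is real and small: a loss of precision on the day-30 continuous DPOAE amplitude. The primary Fisher test is untouched. ECochG and WIN are also untouched, since neither is measured at Visit 3.

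The documents support the direction only. For assumed r of 0.1, 0.3 and 0.5, residual variance falls by 1%, 9% and 25%, before allowing for readings that cannot be used. The gain is negligible if r is near 0.1 or below. It would be tempting to claim a definite number of power points or a set detectable effect, but no DPOAE SD, correlation, effect or power is given to support one, and the analysed sample is below 66 per arm by an unknown margin. This is a worthwhile refinement, not an error that threatens a conclusion.

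**What to change.** In SAP 7.1.2 and Protocol 12.2.2, for the day-30 DPOAE amplitude ANCOVA only:

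- Keep the Visit 2 DPOAE, the noise stratum and all other planned covariates. Add the Visit 3 DPOAE amplitude; do not substitute it for the baseline.
- Use the same ear and frequency summary for the covariate as for the outcome. That summary is not yet defined for the ANCOVA and should be.
- Use the reading only when its documented test time precedes the recorded dose time. Protocol 5.4 already records test time; confirm that dose time is captured, since SAP 6.5 does not name it.
- Set readings that are missing or taken after dosing to the mean of the pre-dose readings and add an indicator.
- State that a pre-dose Visit 3 DPOAE serves as a covariate, and reconcile this with its listing as a between-arm efficacy outcome in Protocol 4.0. Reconcile the 5–10 and 5–30 minute timings as well.

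Make the change before unblinding. It costs one or two degrees of freedom and a little more programming, with no new visits or tests.
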